1) Research design: Quasi-Experimental Design (Non-randomized controlled trial) with experiment and control groups for comparison. Because of ethical considerations on older adults for logistical and economical wise, easy to travel, practical, less budget. Similar studies involving rehabilitation or behavioural interventions in real-world settings have widely used quasi-experimental designs. Studies by MA Handley(2018) and AD Harris (2006) demonstrated reliable outcomes using this approach.

2) Study area: Liaoning Province, China.

3) Study population

i) Reference population: Older adults living in Liaoning.

ii) Source population / sampling pool: Elderly care institutions and rehabilitation centers, Liaoning Province.

iii) Target population: Jinzhou Comprehensive Elderly Care Institution and Rehabilitation Center, Liaoning Province.

iv) Sampling frame: List of members from the two elderly care institution and rehabilitation center; Jinzhou Pension Comprehensive Service Center (JPCSC)), and Jinzhou Rehabilitation Hospital (JRH), Liaoning Province.

4) Subject criteria

Objective No. 1 and 2: To develop and validate the psychomotor rehabilitation nursing plan through content/face validation using the Delphi method.

Inclusion criteria:

- i) Professionals with ≥ 5 years of experience in geriatric care, neurological rehabilitation, cognitive rehabilitation, or psychomotor therapy.
- ii) Academic researchers with publications in related fields.
- iii) Intermediate professional title or above.
- iv) Willingness to participate in multiple Delphi rounds and provide informed feedback.

Exclusion criteria:

- i) Experts without sufficient relevant experience.
- ii) Those unable to commit to the Delphi process.

Objective No. 3: To evaluate the effectiveness of the psychomotor rehabilitation nursing plan in enhancing cognitive function among older adults with mild cognitive impairment. (Experimental and control group)

Inclusion criteria:

- i) Older adults are aged 50 years and above.
- ii) Subjective cognitive complaints from the individual or caregiver.
- iii) Screening for MCI using the Mini-Cog scores between 0-2 (SN Abayomi, 2024).
- iv) Basic language communication, listening, speaking, and understanding skills.

- v) Ability to provide informed consent.

Exclusion criteria:

- i) Diagnosed with severe psychiatric conditions (e.g., schizophrenia, major depressive disorder).

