- ii) It is at the end stage of important functional organ diseases, such as malignant tumors, cardiac failure, etc.
- iii) Limb dysfunction.
- iv) Diagnosed with dementia.

Withdrawal criteria:

- i) Withdrawal of consent by the participant.
- ii) Non-compliance with study requirements (e.g., missing >25% sessions).
- iii) Significant health deterioration affecting participation.

5) Study groups

Experimental group: Older adults with MCI from Jinzhou Rehabilitation Hospital (JRH), with psychomotor rehabilitation nursing plan.

Control group: Older adults with MCI from Jinzhou Pension Comprehensive Service Center (JPCSC), without psychomotor rehabilitation nursing plan.

6) Operational definition:

- i) Mild cognitive impairment (MCI): Mild Cognitive Impairment (MCI) is defined as a condition characterized by noticeable cognitive decline beyond what is expected for an individual's age and education level, but not severe enough to interfere significantly with daily life or independent functioning. It serves as an intermediate stage between normal aging and dementia. (Petersen, R.C., 2004; B. Winblad, 2004).
- ii) Psychomotor therapy (PMT): Psychomotor therapy is a form of therapeutic intervention that focuses on the connection between psychological and motor (physical) functions (Duan Zhouying, Chen Wenhua, 2021).

7) Sample size determination

Objective No. 1 and 2: To develop and validate the psychomotor rehabilitation nursing plan through content/face validation using the Delphi method for older adults with mild cognitive impairment in promoting cognitive function.

A sample size of 8 to 15 respondents has been recommended for Delphi studies, given that smaller samples reduce reliability and bigger ones do not appear to add much value (Kenney et al., 2010). For this study, we aimed to recruit 10-12 participants.

Objective No. 3: To determine the effectiveness of the psychomotor rehabilitation nursing plan in enhancing cognitive function among older adults with mild cognitive impairment .

The sample size was calculated for specific objective 2. It was estimated by using the sample size formula compared with the average of two samples (Ni Ping et al., 2010) . The sample size calculation formula and parameters were as below:

$$N1 = N2 = 2[(t_{\alpha/2} + t_{\beta})S/\delta]^2$$

N1 is the sample content of the experimental group.

N2 is the sample content of the control group.

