S is the estimated value of the standard deviation between the two populations.

δ is the difference between the two averages.

The S and δ were the values of the MMSE scale decided by the researcher based on expert opinion (Liang Jingzhao, Zhi Yanmin, 2022), S= 2.75 , δ = 2.14. The level of significance (α) was 0.05, $t_{0.05/2}= 1.96$, β was 0.10, $t_{0.1}= 1.28$. By substituting the formula, 34 samples were required for each of the two groups.

An estimated 10% was added to the calculated sample size in anticipation of some missing data. The calculated sample size for this study was 76 patients (EG: 38 patients, CG: 38 patients).

8) Sampling method: Purposive sampling

9) Subject setting and participant

PHASE 1 (Delphi-method study for screening and recruitment)

The psychomotor rehabilitation nursing plan design will use Delphi-method which is an integration involving multiple expertise for the PMT development. The participants are the professionals with academic and/or practical experience in Neurology and cognitive training in China's hospitals or universities. There is no agreed method to consider someone an expert in a given field. To facilitate the selection process, it will use a simple point evaluation system. It will include all professionals with a final evaluation of at least 2 points. Regarding academic experience, it will consider the following factors: At least one publication on the

field of cognitive training (1 point) & at least one publication on the field of Neurology (1 point) OR at least one publication on the field of cognitive training in MCI (2 points). Concerning practical experience, it will consider experience in the development of a cognitive training program (1 point). Moreover, it will also consider if the professional had clinical experience in the application of cognitive training (1 point).

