Purposive sampling. Potential participants will be identified through a literature review, existing academic contacts, and a web search for cognitive training programs (for MCI or Neurology or other conditions) and the respective scientific teams. After being evaluated in accordance to the point system previously described, professionals who met the inclusion criteria (2 points or more) will be invited to participate by email. In the initial questionnaire, they will be asked to recommend other professionals who they considered to be experts in the field. Recommended professionals who met the inclusion criteria will be contacted and invited to join the expert panel.

PHASE 2 (Quasi-Experimental design for PMT rehabilitation nursing interventional study)

This experimental method will be used in Quasi-Experimental Design (Non-randomized controlled trial) with experiment and control groups for comparison. Ethics consideration on older adults which would psychologically and emotionally impact in case not selected for experimental group. This research will be carried out in Liaoning Province of China. The rehabilitation nursing intervention will be carried out for older adults with MCI admitted in two China elderly care institutions which the name is Jinzhou Pension Comprehensive Service Center (JPCSC) and Jinzhou Rehabilitation Hospital (JRH). Because of ethical consideration on older adults for logistical and economical wise, easy to travel, practical, less budget. So the experimental group is JRH, and the control group is JPCSC. Purposive sampling, whereby older adults with MCI will be selected and invited to participate the study.

The PMT rehabilitation nursing intervention plan

From Table in the literature review, we can see that most interventions lasted for 3 months. Therefore, older adults will be engaged in a 12-week PMT rehabilitation nursing plan involving 2 phases of relaxation and breathing exercises, face exercises, hand exercises and mind exercises to promote cognitive health. The experimental group will be given interventions, twice a week every Tuesday and Thursday 9-10 am along with the study

intervention. Meanwhile, the control group will be given a standard health education on cognitive health.

Table The Mind-body Exercise of Psychomotor Rehabilitation Nursing Plan

Week	Phase	Intervention methods	Assessment

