Week 0-6 Tuesday Thursday 9:00-10:00 am	Psychomotor function Phase 1	
1.Do relaxation and breathing exercises before and after exercise (10 minutes).
 
2.Blink alternately, bulge left and right cheeks, and improve facial motor function (10 minutes).
 
3.(10 minutes)
  
4.(10 minutes)
  
5.Carry out upper limb gymnastics exercises to improve limb motor function (20 minutes).
	Assessment time is at the baseline (before intervention).
Week 7-12 Tuesday Thursday 9:00-10:00 am	Psychomotor function Phase 2	
1. Do relaxation and breathing exercises before and after exercise (10 minutes).
 
2.(10 minutes)
  
3.(10 minutes)
	Assessment time is at the 12 week (after intervention).

		 
1. (10 minutes)
  
2. Carry out upper limb gymnastics exercises with music to improve limb motor function (20 minutes).
	
--	--	--	--

10) Data collection and Research tool

Phase 1: To develop and validate the psychomotor rehabilitation nursing plan through content/face validation using the Delphi Method for older adults with mild cognitive impairment.

The draft of the PMT rehabilitation nursing plan will be summarized through a literature review. An expert letter questionnaire will be formulated to make the PMT rehabilitation nursing plan more suitable for MCI older adults in China, and specialist consultation will be conducted face-to-face or by email, according to the actual situation. The Delphi method was used to reach a consensus on each program's characteristics, structure, and cognitive training tasks of the PMT rehabilitation nursing plan. A panel of experts was invited to participate in the content validation by answering two rounds of questions (scale and free-text boxes) regarding the program. Changes were made between the rounds according to the results of the first round. The consensus was defined as at least 70% of the experts agreeing on the validity of a characteristic. Experts will be invited to rate the importance and feasibility of the questionnaire items. The experts will be required to provide feedback to us within 2 weeks after receiving the questionnaire. After the first round of expert inquiry, the PMT

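### Withdrawal for missed sessions would act mainly on the experimental group, and no visible text says that those withdrawn are still assessed or analysed at 12 weeks

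*Combined protocol and SAP*

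**What the plan says.** All references are to the combined protocol and SAP.

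- **Section 4, withdrawal criteria.** Criterion ii is "Non-compliance with study requirements (e.g., missing >25% sessions". Criterion i is withdrawal of consent and criterion iii is significant health deterioration. They fall under Objective 3, headed "enhancing cognitive function among older adults with mild cognitive impairment. (Experimental and control group", so they cover both groups. The section does not say whether withdrawal is from sessions, from assessment or from analysis.
- **Intervention plan.** "The experimental group will be given interventions, twice a week every Tuesday and Thursday 9-10 am", for 12 weeks. By contrast, "the control group will be given a standard health education on cognitive health", with no number, length or frequency of sessions. Section 5 defines that arm as "Control group: Older adults with MCI from Jinzhou Pension Comprehensive Service Center (JPCSC), without psychomotor rehabilitation nursing plan".
- **Section 10, Phase 2.** Questionnaires are given at baseline and at 12 weeks only.
- **Section 11, Objective 3.** The named test is the paired t-test. No analysis population, missing-data method or follow-up of withdrawn participants is stated. The dummy tables give n = 76 both before and after.
- **Section 7.** "The calculated sample size for this study was 76 patients (EG: 38 patients, CG: 38 patients", after adding 10% for expected missing data.

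**The concern.** An attendance rule needs a count of scheduled sessions. Only the experimental group has one, so as described the example in criterion ii would act mainly on that group. If withdrawal also ends assessment, a low attender has no 12-week score and cannot enter a paired test. The experimental group would then be selected on behaviour after entry, with no matching selection among controls.

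This could shift the experimental group's before-after change and any difference from controls. The shift favours the intervention if low attenders would have scored worse. That is plausible, but the documents do not show it. It goes the other way if they would have scored better. A larger sample does not remove it, and a 12-week assessment that was not done cannot be recovered later.

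**Working it through.** **1. The plan's own sample size (section 7).** Inputs: S = 2.75, δ = 2.14 (MMSE), 1.96 and 1.28.

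2 × [(1.96 + 1.28) × 2.75 / 2.14]² = 34.67 per group. The plan states 34. Then 34 × 1.10 = 37.4, so 38 per group and 76 in total. The stated figures reproduce, apart from 34.67 being rounded down. The 10% allowance applies equally to both groups.

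**2. The attendance threshold.** 12 × 2 = 24 sessions and 25% of 24 is 6, so more than 25% means 7 or more missed. The table labels ("Week 0-6 Tuesday Thursday 9:00-10:00 am", then weeks 7 to 12) could be read as 13 weeks: 26 sessions, 25% = 6.5, again 7 or more.

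**3. Illustrative size.** The documents give no attendance rate. Assumptions: p is the share of the experimental group lost beyond any similar loss in controls; attenders gain 2.14, low attenders gain nothing, and controls do not change. The target is the effect in everyone entered. Units are the MMSE planning scale, whereas the trial's cognitive outcome is the MoCA.

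*Experimental group's change, or difference from controls.* Everyone analysed: (1 − p) × 2.14. Attenders only: 2.14. Overstatement: p × 2.14.

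| p | people (38p) | overstatement, points | % of δ |
|---|---|---|---|
| 5% | 1.9 | 0.107 | 5% |
| 10% | 3.8 | 0.214 | 10% |
| 20% | 7.6 | 0.428 | 20% |

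*One pooled before-after test of both groups, as the dummy tables are laid out.* Everyone analysed: (1 − p) × 2.14 / 2. Low attenders dropped: (1 − p) × 2.14 / (2 − p). The ratio is 2 / (2 − p), so the pooled change is overstated by the proportion p / (2 − p).

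| p | everyone | low attenders dropped | overstatement, points | % of pooled change |
|---|---|---|---|---|
| 5% | 1.017 | 1.043 | 0.026 | 2.6% |
| 10% | 0.963 | 1.014 | 0.051 | 5.3% |
| 20% | 0.856 | 0.951 | 0.095 | 11.1% |

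In proportion this is about half the first table. In points it is about a quarter, because unchanged controls already halve the pooled change.

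**4. Power cost of keeping low attenders.** This uses a between-group comparison, which section 7 assumes ("It was estimated by using the sample size formula compared with the average of two samples"), two-sided 5%, SD 2.75, normal approximation: power = Φ(effect / SE − 1.96), with SE = 2.75 × √(1/n₁ + 1/n₂).

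| low attendance | dropped (effect 2.14) | kept, gain nothing (38 v 38, SE 0.631) | kept, gain half |
|---|---|---|---|
| 10% | 34 v 38, SE 0.649: 90.9% | effect 1.926: 86.3% | effect 2.033: 89.7% |
| 20% | 30 v 38, SE 0.672: 89.0% | effect 1.712: 77.4% | effect 1.926: 86.3% |

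**The case against.** A reader might infer that the plan excludes low attenders from the analysis, and in the experimental group only. The documents do not say that. The 25% figure is an example, withdrawal is undefined, and the criteria cover both groups. The controls' health education could be given in sessions that are not described. The dummy tables' n of 76 after the intervention equals full enrolment and could mean that everyone is to be analysed. The study flowchart and the consent pages are not in the copy reviewed and might settle the matter.

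Most of this stands as a limit on certainty. It does not remove the point. The 76 is a placeholder, it says nothing about withdrawn participants, and it conflicts with the 10% allowance for missing data.

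A second objection is that the effect in attenders is a legitimate target. The plan names no target population for analysis, but Objective 3 asks about effectiveness among older adults with mild cognitive impairment, not only among those who attend. An attenders-only experimental group also has no counterpart among controls.

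Third, the bias may be small beside the confounding of group with institution. That is fair: this change leaves that confounding untouched. Loss tied to attendance is a separate problem, and one that can be avoided.

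**Conclusion.** The point holds as an unstated rule with a likely consequence, not as a stated exclusion. On the ordinary reading of the visible text, low attenders would leave the paired analysis mainly from the experimental group, and this can bias the result.

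The size is unknown. The figures of 5%, 10% and 20% of the planned difference, and about half those proportions in a pooled test, rest wholly on assumed loss rates and on low attenders gaining nothing. A gap wider than 2.14 points would require them to do worse than simply missing the benefit, so the illustration stops there. Nor do the documents support the stronger claim that the intervention's effect will be overstated, because the direction depends on how low attenders would have scored.

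**What to change.** Leave any rule on stopping sessions as it is. Add to section 4:

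> Meeting criterion ii, alone or together with criterion iii, does not by itself end follow-up. Every participant who has not withdrawn consent is invited to the 12-week assessment and is analysed in the group entered. Sessions attended are recorded.

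In the section 11 results tables, replace the fixed n of 76 after the intervention with the number entered and the number assessed at 12 weeks, by group. Anyone invited but not assessed still drops out of a paired test, so these counts are needed to show how much loss remains. If the flowchart already covers follow-up, repeat it in section 4.

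Do not use a 75%-attendance subset as a between-group sensitivity analysis, because controls have no stated session schedule. If it is reported at all, label it as a descriptive result for the experimental group.

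Cost: the added wording, an attendance log, and one already planned assessment of no more than 60 minutes for each low attender (about 2 to 8 people if 5% to 20% of 38). The main downside is dilution. If low attenders gain nothing, power is about 86% rather than 91% at 10% low attendance, and about 77% rather than 89% at 20%. The loss is smaller if they gain part of the effect.

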rehabilitation nursing program will be modified, deleted and supplemented based on the experts' scores and opinions on the items, so as to determine the second round of expert inquiry questionnaires and conduct the second round of expert inquiry. There will be a 3-week interval between the first and second rounds. After receiving the questionnaires from the experts, the inquiry results will be summarized and statistically analyzed until the experts' opinions reach a consensus, and the entire inquiry process will be terminated.

The duration of participant involvement in the Delphi method will be approximately 6 – 10 weeks in total, depending on the number of rounds required to reach expert consensus. Each Delphi round will require participants to complete the questionnaire, which is estimated to take 20 – 30 minutes per round. Between rounds, there will be a 1 – 2-week interval for data analysis and feedback preparation. While we anticipate achieving consensus within two rounds, a third or fourth round may be necessary if the responses require further refinement. In such a case, participants will be informed in advance, and their continued involvement will be requested. We will strive to minimize the burden on participants while ensuring robust and reliable results.

Phase 2: To evaluate the effectiveness of the psychomotor rehabilitation nursing plan among older adults with mild cognitive impairment.

The data will be collected from January 2025 to December 2025 in China's older adults care institutions. The data collection form was created by the researcher to record general information about older adults, such as age, gender, education level, family history of dementia, marital status, personal annual income, chronic disease. It will take no more than 5 minutes. Then, It will conduct questionnaire surveys before the intervention (baseline) and after the intervention (12 weeks). The questionnaires involved include MoCA, which has 11 questions and takes about 10 minutes; PANSS, which has 30 questions and takes about 20 minutes; HAMA-14, which has 14 questions and takes about 10 minutes; HAMD-17, which has 17 questions and takes about 15 minutes. All questionnaires will take no more than 60 minutes. Due to ethical issues, the names of the elderly participating in this study are only used for data collection, and their identity information will not be disclosed.

Data/Specimen handling:

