2.6 Phase 2 -Task 1	Do relaxation and breathing exercises before and after exercise (10 minutes).			
2.7 Phase 2 -Task 2	Hand muscle training/flexibility training/hand-eye coordination/improved circulation: The older adults held and rotated two balls with one hand according to instructions (10 minutes).			
2.8 Phase 2 -Task 3	Hand fine training/flexibility training/hand-eye coordination/endurance and concentration training (10 minutes).			
2.9 Phase 2 -Task 4	Hand-eye coordination training/cognitive ability training/fine skills training/teamwork and social interaction training (10 minutes).			
2.10 Phase 2 -Task 5	Carry out upper limb gymnastics exercises with music to improve limb motor function (20 minutes).			

Objective No. 3: To evaluate the effectiveness of psychomotor rehabilitation nursing plan in enhancing cognitive function among older adults with mild cognitive impairment.

Data entry and analysis will be performed using SPSS 28.0 software. Descriptive statistics will be used to summarize the general information of older adults. Numerical data will be presented as mean (SD) or median (IQR) based on their normality distribution. Categorical data will be presented as frequency (%). The comparison of scores of various scales are based on paired t-test statistical methods. The P value <0.05 will be considered to indicate statistically significant with 95% confidence interval (CI).

Expected result (Dummy Table): The effect assessment of the PMT rehabilitation nursing plan

Table Comparison of cognitive status between two groups ($\bar{x} \pm s$, scores)

Assessment	Before (n = 76)	After (n = 76)	Diff (95% CI)	t	P
Orientation					
Registration					
Attention and Calculation					
Recall					
Language and Praxis					
MoCA total score					

[figure not shown]
Table Comparison of psychological status between two groups ($\bar{x} \pm s$, scores)

Assessment	Before (n = 76)	After (n = 76)	Diff (95% CI)	t	P
Positive scale					
General psychopathology scale					
Negative scale					

Table Comparison of mental rehabilitation status between two groups ($\bar{x} \pm s$, scores)

Assessment	Before (n = 76)	After (n = 76)	Diff (95% CI)	t	P
Mood-related signs					
Behavioral disturbance					
Cyclic functions					
Ideational disturbance					

Study flowchart

Gantt chart & milestone

Research Activities	2024				2025				2026			
	Jan-Mar	Apr-Jun	Jul-Sep	Oct-Dec	Jan-Mar	Apr-Jun	Jul-Sep	Oct-Dec	Jan-Mar	Apr-Jun	Jul-Sep	Oct-Dec
Preliminary discussion												

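### The plan makes no provision for scoring participants withdrawn for health deterioration, so the before-after comparison could rest on completers selected by their health

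*Combined protocol and SAP*

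**What the plan says.** Section 4 (Subject criteria, Objective No. 3) is headed for the experimental and control groups together. It gives three grounds for withdrawal: withdrawn consent, non-compliance such as missing more than a quarter of sessions, and "Significant health deterioration affecting participation". The third ground is not defined further, and the plan does not say whether anyone withdrawn under it is still assessed.

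Section 10 (Phase 2) schedules the questionnaires twice, at baseline and at 12 weeks. Section 11 (Objective No. 3) names one method: "The comparison of scores of various scales are based on paired t-test statistical methods". It gives no analysis set, missing-data method or sensitivity analysis. The dummy tables show 76 participants both before and after the intervention.

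The only mention of missing data for Objective 3 is in section 7: "An estimated 10% was added to the calculated sample size in anticipation of some missing data".

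**The concern.** A paired t-test uses only people who have both scores. There is no visit between baseline and week 12 and no provision for assessment after withdrawal, so a participant withdrawn for poor health would ordinarily have no second score and would drop out of the comparison. The reason for the loss is then a worsening of health, not chance.

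Such worsening may be related to the outcomes. The link is plausible for three scales that rate bodily symptoms directly, and on all three a higher score is worse:

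- HAMA-14 has cardiovascular, respiratory and somatic items.
- HAMD-17 has items on somatic symptoms, weight loss, retardation and reduced activity.
- PANSS has items on somatic concern and motor retardation.

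For MoCA the link is less direct. If it exists, the average change among completers is shifted toward improvement, and some of the deterioration that the study hopes to prevent is recorded as missing data. Enlarging the sample by 10% leaves that shift unchanged.

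**Working it through.** **1. The plan's own figure.** Section 7 gives S = 2.75, δ = 2.14, and multipliers 1.96 and 1.28. Then 2 × [(1.96 + 1.28) × 2.75 / 2.14]² = 2 × (8.91 / 2.14)² = 34.67. The plan states 34. Adding 10% gives 34 × 1.1 = 37.4, so 38 per group and 76 in total, as stated. The allowance is 38 − 34 = 4 per group, or 8 of 76.

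**2. Model for the loss.** Change is scored so that positive means improvement, and is normal with true mean zero. Each person also has a withdrawal index with correlation ρ to that change. The k people lowest on the index are removed and a two-sided 5% paired t-test is run on the rest (20,000 simulated trials per setting). The values of ρ are assumptions, since the documents give none.

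For a lost fraction d, the bias in SDs of change is approximately ρ × φ(z_d) / (1 − d), where z_d is the d-quantile of the standard normal distribution and φ its density. At d = 0.10 this is ρ × 0.195:

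- ρ = 0.3: 0.3 × 0.195 = 0.06 SD
- ρ = 0.5: 0.5 × 0.195 = 0.10 SD
- ρ = 1: 0.20 SD

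**3. Chance of a significant improvement when there is none** (nominal 2.5%; SD of change 2.75, see step 4):

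| Lost | ρ = 0 | ρ = 0.3 | ρ = 0.5 | ρ = 1 (ceiling) |
|---|---|---|---|---|
| 2 of 38 | 2.5% | 3.8% | 5.1% | 11.8% |
| 4 of 38 | 2.6% | 5.4% | 8.8% | 28.0% |
| 4 of 76 | 2.7% | 4.8% | 6.9% | 19.3% |
| 8 of 76 | 2.5% | 7.1% | 13.8% | 48.7% |

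The rows with 38 treat one group alone. The rows with 76 follow the pooled column headings of the dummy tables. If losses reached 20%, the rates at ρ = 0.3 to 0.5 would be 8.9% to 17.2% (8 of 38) or 12.4% to 28.6% (15 of 76).

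**4. In scale points.** The SD of change is S × √(2(1 − r)), where r is the correlation between baseline and week 12. The documents do not give r. Taking r = 0.5 gives 2.75, and r = 0.8 gives 1.74. With 8 of 76 lost:

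- SD 2.75: bias 0.16 to 0.28 points at ρ = 0.3 to 0.5; 0.55 at ρ = 1
- SD 1.74: bias 0.10 to 0.17 points at ρ = 0.3 to 0.5; 0.35 at ρ = 1

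Against δ = 2.14, the range 0.16 to 0.28 is 7% to 13%. S and δ are MMSE values while the cognitive outcome is MoCA, so this comparison is only a rough guide.

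**5. If the true mean change is a decline.** With a true mean of −0.5 points, SD of change 2.75 and 8 of 76 lost, the completers' mean is −0.34 at ρ = 0.3 and −0.23 at ρ = 0.5. Here the loss mostly hides decline.

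**6. Comparison of change between groups, 38 per group (SD of change 2.75).** If both groups lose 10% in the same way, the bias is about zero at every ρ. If only the experimental group loses 10%, the bias is 0.16 to 0.27 points at ρ = 0.3 to 0.5 (0.55 at ρ = 1), and false benefit is found in 4.5% to 6.4% of trials (15.3% at ρ = 1).

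**The case against.** The strongest reply is that the plan nowhere says withdrawn people go unscored; it is silent. It is also right that the third ground concerns health in general. The ethics section names falls, injury and frustration as risks, and a fall could end participation without any cognitive decline. If withdrawal is unrelated to change, there is no bias. Both points stand, and they make this a conditional concern.

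A reader might go further in four ways that the documents do not support:

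- **That the rule falls only on the experimental group and so favours PMT.** The criteria are headed for both groups. Participation can also cover the control group's health education and the assessments themselves. Only the experimental group has a stated session schedule, so uneven loss is possible, but it is not established.
- **That the false-positive rate would be 28% or 49%.** Those figures need exactly the worst changers to be lost, and are a ceiling.
- **That losses cannot exceed 10%.** The 10% is a planning allowance and not a cap.
- **That 76 in the after column shows how losses are handled.** The tables are labelled as dummies, so the figure shows only that the template was not adjusted for the loss expected in section 7.

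It can also be said that the attendance ground leaves the same gap. That is true, and one wording can cover both. Dealing with attendance alone would still leave the loss that is selected on health.

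**Conclusion.** The concern holds in conditional form. The plan has a withdrawal ground tied to health, no provision for a later score, and a test that needs both scores. Read in the ordinary way, this produces an analysis of completers selected by health.

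Under the stated assumptions (about 10% lost, no true change, correlation 0.3 to 0.5), the within-group bias is about 0.06 to 0.10 SD. The false-improvement rate is roughly two to three and a half times nominal with 38 participants, and three to five and a half times with 76. That is enough to make a small change look significant. Even the ceiling of 0.55 points is well short of the planned 2.14, so the bias alone could not produce an effect of the planned size.

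The size is uncertain because neither the correlation nor the number lost is given. The gap itself does not depend on either figure and should be closed.

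**What to change.** In section 4, state that the third ground ends participation in sessions only, with the decision to stop sessions left to the investigator. State that these participants, in both groups, are still assessed at week 12 if they consent and can be tested, and are analysed in their original group. The same sentence can cover the attendance ground.

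In section 11:

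- Specify a between-group comparison of change, which is not there now.
- Add a rank-based sensitivity analysis of that comparison, giving the worst rank to anyone who cannot be tested because of deterioration or death.
- Report withdrawals by reason and group.
- In the tables, replace the after-intervention count of 76 with the number actually scored in each group.

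The cost is a few more week-12 assessments of up to 60 minutes (about 8 if losses match the allowance), one extra analysis, and the text for the between-group comparison. There is some burden on participants in poor health, who remain free to decline. The estimated benefit may be smaller once their scores are included.
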